## 2. Specific Aims:

- a. **Specific Aim 1:** To determine the burden of CT, NG infections and correlates of infection among *asymptomatic* pregnant women in Gaborone, Botswana.
  - i. 1(a): Use diagnostic testing to estimate the prevalence of CT/NG infections at the 1st antenatal care visit, a 3rd trimester visit, and the 1st postnatal care visit; and estimate the incidence of infections between those visits.
  - ii. 1(b): To assess the correlates of infection, including sociodemographic and behavioral factors (e.g. alcohol use), obstetric and medical information (e.g. HIV status), and sex partner characteristics.
- b. **Specific Aim 2:** To compare longitudinal neonatal outcomes for pregnant women tested & treated for CT/NG infections during antenatal care with women who received standard antenatal care.
  - i. 2(a): To estimate the frequency of vertical transmission of CT/NG infections and subsequent neonatal outcomes (e.g. ophthalmia neonatorum) and the association with maternal testing and treatment during antenatal care.
  - ii. 2(b): To assess independent factors that may be predictive of adverse neonatal outcomes and control for these factors in the analysis. Exposure measures will include maternal sociodemographic and behavioral factors (e.g. alcohol use), obstetric and medical information (e.g. HIV status), partner characteristics, and adverse perinatal outcomes (e.g. low birth weight).

- c. **Specific Aim 3:** To assess the burden of infection and markers of inflammatory response to CT/NG infection during pregnancy and associations with vertical transmission of CT/NG.
  - i. 3(a): To test immunologic factors associated with vertical transmission of CT/NG by describing concentrations of genital inflammatory cytokines in participants who test positive for CT/NG.
  - ii. 3(b): To determine the association between the Xpert® CT/NG assay's pathogen-specific cycle threshold value (Ct), a possible marker for burden of infection, and vertical transmission of CT/NG to neonates.
  - iii. 3(c): To evaluate the frequency and distribution of Sample Adequacy Control (SAC) cycle threshold values (Ct) from the Xpert® CT/NG assay, which are a measure of tissue inflammation, and evaluate any correlations with the transmission of CT/NG to neonates.
- d. **Specific Aim 4:** To determine the acceptability, feasibility, and costs of implementing point-of-care (PoC) syphilis testing and treatment among pregnant women in Gaborone, Botswana.

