**Recruitment/Eligibility:** Women will be similarly recruited and enrolled, and eligibility criteria are identical to those in the STI testing group (see Aim 1). Those who are ineligible due to STI-related symptoms will be flagged and identified for healthcare providers to assess for syndromic management (standard care). All eligible patients will be invited to participate, and those providing informed consent will be enrolled. The comparison group will receive the standard of care for management of STIs during antenatal care with additional IPV screening and partner services offered to those in Aim 1. As in Aim 1, a data collection instrument will be used to collect sociodemographic and behavioral factors, and obstetric/medical information, and data will be abstracted from the patient-held and clinic records. All mothers will be provided with informed consent for their neonate’s participation at enrollment.

Postdelivery, study staff will provide an updated verbal consent to mothers to collect and tests neonatal specimens.

**Laboratory testing:** All participants will test for CT/NG infection using the Xpert® CT/NG assay at the first postnatal visit using self-collected swabs. Women testing positive will receive antimicrobial treatment with options for partner treatment described in Aim 1. For neonates of mothers testing positive for CT/NG, the study follow-up nurse will collect ocular and nasopharyngeal swab samples for testing of CT/NG transmission using the Xpert® CT/NG assay. Studies have demonstrated the efficacy of PCR tests for infant diagnosis using ocular and nasopharyngeal swabs. Infants testing positive will receive treatment according to Botswana guidelines (20mg/kg of azithromycin (liquid formulation) for CT, injection of 50mg/kg of ceftriaxone for NG) and referrals. Efforts will be made to provide same-day results.

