Title: The diagnosis and treatment of *Chlamydia trachomatis* and *Neisseria gonorrhoeae* in pregnant women to prevent adverse neonatal consequences.”

CT/NG to neonates; and 3(c): To assess the frequency and distribution of Sample Adequacy Control (SAC) cycle threshold ( $C_t$ ) values from the Xpert® CT/NG assay, which may be a marker of inflammation, and evaluate correlations with the transmission of CT/NG to neonates.

**Recruitment/Eligibility:** Eligibility criteria for the comparison group are identical to those in Aims 1 and 2. Data will only be collected from participants in the STI testing group.

**Specimen Collection, Transport, Processing and Storage:** A self-collected swab for cytokine measurement will be collected at the baseline, third trimester, and first postnatal care visit and stored at -80°C. A peripheral blood sample (2-4mL) will be collected at the baseline, third trimester, and postnatal study visits. The blood sample will be processed and aliquots of EDTA plasma will be stored at -80°C. The swabs and plasma samples will be transported in dry ice to Stanford University for processing. Luminex will be used to measure the concentrations of 48 cytokines in the 48-plex assay (including IL-1 $\alpha$ , IL-1 $\beta$ , IL-6, IL-7, IL-8, IL-10, granulocyte macrophage colony- stimulating factor [GM-CSF], interferon- $\gamma$  inducible protein [IP]-10, monocyte chemoattractant protein [MCP]-1, MIP-1 $\alpha$ , MIP-1 $\beta$ , and tumor necrosis factor [TNF]- $\alpha$ ). These cytokines were selected based on previously identified associations with genital infection. Additionally the pathogen-specific and SAC Ct results will be automatically generated for each self-collected vaginal sample tested using the Xpert® CT/NG assay at delivery.

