## 5. Characteristics of the Subject Population:

### a. Number of subjects / Sample size:

Pregnant women attending their first ANC care visit at 27 weeks gestation or less. Participants must be 15 years of age and not treated with azithromycin, doxycycline, cefixime, or ceftriaxone in the past 30 days.

**Specific Aim 1 (STI testing group):** We will recruit 250 study participants for CT and NG testing.

**Specific Aim 2 (Standard of care comparison group):** We will recruit 250 antenatal patients from designated study ‘standard of care’ clinics who will be enrolled as a comparison group receiving the standard care with additional IPV and partner services and postnatal care testing (Total N=500). Among participants who test positive during postnatal care, we will offer infant testing (Estimated N=30 infants).

For Specific Aims 1 & 2, study staff will remain at study clinics during operating hours for the duration of the recruitment period. We will consecutively screen all pregnant women for eligibility and offer enrollment to all eligible women.

**Specific Aim 3 (Inflammatory markers):** We will include women in the STI testing group (Estimated N=250).

**Specific Aim 4:** We will enroll an additional 400 antenatal patients for the PoC syphilis sub-study (200 will receive the standard of care and 200 will be offered PoC syphilis testing in addition to the standard of care)

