- Specimens for CT/NG and syphilis testing will be processed onsite at the antenatal clinics by study personnel.
- Specimens for *Trichomonas vaginalis*, bacterial vaginosis, and/or *Mycoplasma genitalium* testing will be stored for up to 24 months at BHP.
- The self-collected swabs and EDTA plasma aliquots for cytokine measurement will be stored at -80 C. The swabs and EDTA plasma will be transported in dry ice to Stanford University for processing. Luminex will be used to measure the concentrations of 48 cytokines (including IL-1a $\pm$ , IL-1b $\leq$ , IL-6, IL-7, IL-8, IL-10, granulocyte macrophage colony- stimulating factor [GM-CSF], interferon- $\gamma$  inducible protein [IP]-10, monocyte chemoattractant protein [MCP]-1, MIP-1a $\pm$ , MIP-1b $\leq$ , and tumor necrosis factor [TNF]-a $\pm$ ). These cytokines were selected based on previously identified associations with genital infection.(34) Additionally the pathogen-specific and SAC Ct results will be automatically generated for each self-collected vaginal swab sample tested using the Xpert CT/NG assay at the first postnatal visit.

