Prevalence of each STI will be measured as the proportion of individuals testing positive for a given STI divided by the number of individuals tested at each time point. Exact binomial 95% confidence intervals for prevalence will be estimated. Incident infections will be identified when a participant tests negative for an STI during her first ANC visit and positive for an STI during follow-up visits. Time at risk will be the length of time between the first test date and the positive test date. Correlates of CT/NG infections will be identified using both bivariate analyses and multivariate analyses.

Our primary outcome (mother-to-child transmission of CT and NG) and secondary outcomes (composite of preterm birth and/or low birth weight, and prevalence of maternal CT/NG infection at delivery) will be assessed using intention to treat analysis at the clinic level. We will conduct both unadjusted and adjusted analyses, including risk factors for maternal STI and neonatal infection that may be imbalanced between the testing and standard-of-care clinics. Effect measures will be estimated with 95% confidence intervals. All analyses will be carried out using the latest version of Stata statistical software (17.0 or higher; College Station, TX, USA).

To assess immune/inflammatory markers, multiple logistic regression models will be developed in an iterative process to identify individual cytokines and groups of cytokines associated with mother-to-child

transmission of CT/NG, preterm birth, and low birth weight. Additionally, we will identify plasma cytokine signatures that classify study participants with or without preterm birth/low birth weight infants.(1) We will define three equal frequency tertiles or “bins” (low, medium, and high), using all plasma samples. Next, we will use the VSURF R package, a random forest method to select the most predictive cytokines to differentiate samples from participants with and without preterm birth/low birth weight infants.(2) From these, we will build a decision tree to classify the samples. To better calibrate the accuracy of the decision tree, we will perform permutation testing.

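### Cytokines are measured only in the testing arm, where the plan expects about 1.6 transmissions, too few for the planned cytokine-transmission models; the arms used for Ct and SAC and the unit of the birth-outcome classifier also need stating

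*Protocol*

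**What the plan says.** **Cytokines.** Protocol section 3 (Specific Aim 3), section 6 and section 7a take vaginal swabs and plasma for a 48-plex cytokine assay from the STI testing group only, at baseline, third trimester and the postnatal visit. Section 5a sizes the aim accordingly: "We will include women in the STI testing group (Estimated N=250". Sub-aim 3(a) is "To test immunologic factors associated with vertical transmission of CT/NG by describing concentrations of genital inflammatory cytokines in participants who test positive for CT/NG". The SAP (Statistical analysis) goes further. It plans multiple logistic models, developed iteratively, to find single cytokines and groups of cytokines associated with transmission, preterm birth and low birth weight.

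**Ct and SAC (sub-aims 3(b) and 3(c)).** Sections 3 and 6 call these a secondary analysis of maternal testing at the first postnatal visit under Aim 2. Under Aim 2 and section 7a all participants in both arms have that test. Section 7a adds: "Additionally the pathogen-specific and SAC Ct results will be automatically generated for each self-collected vaginal swab sample tested using the Xpert CT/NG assay". Yet the Recruitment/Eligibility paragraph of Aim 3 says without qualification: "Data will only be collected from participants in the STI testing group". Infants are swabbed only if the mother is positive: "For neonates of mothers testing positive for CT/NG, the study follow-up nurse will collect ocular and nasopharyngeal swab samples". The SAP contains no Ct or SAC analysis.

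**Classifier.** The SAP sets out to classify participants by preterm birth/low birth weight. It forms cytokine tertiles "using all plasma samples", selects cytokines with VSURF and builds a tree that classifies the samples. It then says: "To better calibrate the accuracy of the decision tree, we will perform permutation testing".

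**The concern.** The outcome of the cytokine-transmission models is neonatal infection in the arm where the intervention is meant to prevent it. The better testing and treatment work, the fewer events those models have. If the plan's own assumptions hold, the promised transmission signature cannot be estimated. Anything reported would come from an iterative search over 48 markers on one or two cases.

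The other two parts are gaps in specification. If the Ct and SAC population is settled only after the data are seen, the analysis could rest on about one eighth of the transmissions that the study will already have recorded. If the classifier treats a woman's repeated samples as independent, its permutation p-value may be too small. A postnatal sample also cannot predict an outcome that has already occurred.

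**Working it through.** **The plan's own figures.** SAP, Sample size: control rate 0.10 × 0.50 = 5%; intervention rate 0.7% (a reduction of 1 − 0.7/5 = 86%); 250 × 0.93 = 232.5, so 232 evaluable women per arm. The stated power of 80.7% is reproduced by the one-sided, continuity-corrected two-proportion formula (80.69%). Exact one-sided Fisher power from the same inputs is 85.2%. The inputs are therefore taken as the plan's working assumptions.

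**1. Transmissions available to the cytokine models**

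| Basis, testing arm | Expected events | P(0) | P(at most 1) |
|---|---|---|---|
| SAP rate: 232 × 0.007 | 1.62 | 20% | 52% |
| 30 infants, 25 from the other arm: (30 − 25) × 0.5 | 2.5 | 8% | 29% |
| 30 infants, 23.2 from the other arm: (30 − 23.2) × 0.5 | 3.4 | 3% | 14% |
| No effect of testing: 232 × 0.05 | 11.6 | <0.1% | <0.1% |

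The probabilities are binomial with n = 232. The middle rows start from section 5a ("Among participants who test positive during postnatal care, we will offer infant testing (Estimated N=30 infants") and subtract standard-care positives at 10% of 250 or of 232. At 1.62 events the chance of five or fewer is 99%. Spread over 48 cytokines, 1.62 events is 1.62/48 = 0.03 per marker. Even 11.6 events is 11.6/48 = 0.24 per marker. The extra antenatal swabs from a standard-care sub-sample (section 7a) do not help: they are immediately de-identified and not designated for cytokines.

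**2. Ct and SAC: what the choice of arm changes**

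- Testing arm only: 1.62/0.5 = 3.2 positive mothers and 1.6 transmissions on the SAP rate, or 5 to 6.8 positive mothers on the 30-infant estimate.
- Both arms: 23.2 + 3.2 = 26.4 positive mothers and 11.6 + 1.6 = 13.2 transmissions, about eight times as many (13.2/1.62).

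For precision, the 95% half-width for a difference in mean Ct is t(0.975, df) × √(1/a + 1/b) in SD units. Counts are rounded and all positives pooled.

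- 2 v 2 (testing arm): 4.30 × 1 = 4.3 SD.
- 3 v 4 (testing arm, high end): 2.57 × √(1/3 + 1/4) = 2.0 SD.
- 14 v 12 (both arms, arm as covariate): 2.07 × 0.393 ≈ 0.8 SD. Simulated power is 48% for a 0.8 SD shift.

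Pathogen-specific Ct splits the 26 mothers into CT and NG, so each analysis will be less precise than the last line.

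**3. Classifier.** Up to three plasma samples per woman (baseline, third trimester, postnatal) share one birth outcome. The SAP names participants as the target but samples as what is binned and classified. It does not say which visits enter, what is permuted, or which statistic beyond accuracy is calibrated. Permuting sample labels breaks the link between a woman's samples, so the reference distribution is too narrow when those samples are correlated.

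The size is not fixed by the documents. A simulation used pure-noise cytokines with these assumed inputs: 232 women with three pooled samples each, an 18% outcome rate, within-woman correlation 0.5, and a simple tree without VSURF. At a nominal 5%, permuting samples gave false-positive rates from 0% (plain accuracy, depth-2 tree) to 53% (Gini criterion, depth-2 tree). Permuting women gave 0 to 6%.

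**The case against.** **On the cytokine models.** The 0.7% is a planning rate, not an observation; more events would arise if testing worked less well. The SAP lists cytokines as secondary, and 3(a) already names description as its method. A minimum-event rule or an exploratory label might be enough. The first points are fair and keep this off the critical path, but even with no effect of testing there are 11.6 events for 48 markers, so an iterative multivariable search is not sound at any plausible count.

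**On Ct and SAC.** The natural reading is that the limiting sentence governs new Aim 3 specimens, since a secondary analysis collects nothing, and that the 250 refers to inflammatory markers. This largely stands. The documents point to both arms; what remains is an unqualified sentence and a silent SAP.

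Two stronger readings are tempting. One is that on testing-arm data no exact two-sided rank test of Ct could reach p < 0.05. The smallest attainable value, 2/C(m,k) minimised over k, is 0.67, 0.33, 0.20, 0.10 and 0.057 for 3 to 7 positive mothers. But the number of mothers is not fixed: with 8 it is 2/70 = 0.029, and the chance of 8 or more is 2%, 13% or 37% at expected counts of 3.2, 5 or 6.8. The plan names no test either. The other is that including negative mothers makes the SAC analysis well powered (simulated power 83% for 0.8 SD, 14 v 450). That contrast is mostly infected against uninfected women whose infants are never tested, so it does not answer 3(c).

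**On the classifier.** A reader might infer that the permutation test will be inflated. The documents do not support that: sample-level permutation is not stated, the phrase about all plasma samples attaches to the tertile cut-points, and plain accuracy, the closest match to the SAP's wording, showed no inflation with the shallow tree. What stands is that the unit and the visits are unspecified.

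**Conclusion.** The cytokine-transmission models cannot be supported by the data the plan expects: about 1.6 events on the SAP's rate, 2.5 to 3.4 on the protocol's infant estimate, and 11.6 if testing does nothing. This rests on the SAP's 10%, 50% and 0.7% and on 232 evaluable women, and is the firm part of the point.

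It does not extend to the preterm birth and low birth weight models: the documents give no rates for those outcomes, so no shortage of events is shown.

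The Ct and SAC population is a conflict of wording. It matters because the narrow reading would cut expected transmissions from about 13 to about 1.6. Precision stays limited even with both arms.

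The classifier gap is real, but its effect is undetermined and can be nil.

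No primary conclusion is affected. The changes should be made before analysis.

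**What to change.** 1. **SAP, Statistical analysis.** Replace the cytokine-transmission models with an exploratory description of concentrations in positive mothers by transmission status, following the method in 3(a). Promise no test of association with transmission, and soften the aim's testing language to match. Keep the preterm birth and low birth weight models.
2. **Protocol section 3 (Aim 3) and section 5a; SAP.** State that only the cytokine specimens are limited to the testing group. Analyse postnatal Ct and SAC values from both arms, with arm as stratum or covariate, as exploratory estimates with confidence intervals. Restrict transmission contrasts to mothers whose infants were tested. Add this analysis to the SAP.
3. **SAP, classifier.** Use only samples drawn before delivery, one visit at a time or grouped by woman. Permute women's labels, repeat variable selection and tree building in every permutation, and name the statistic.

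**Cost.** Wording and some computing; no new specimens or assays. The plan gives up the promise of a cytokine signature for transmission. A third-trimester classifier omits women who deliver before that visit. Both-arm Ct and SAC data mix mothers tested and not tested antenatally, which is why arm must be in the analysis.

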**Reporting and Treatment:** PoC Results: All participants will receive results in person, on the same day as testing. Treatment: Appropriate clinical staff will provide treatment per the Botswana MoH STI treatment protocols (see Treatment section below). Test results will be recorded in the participant obstetric record, clinic records, as well as into the study data form. Partner Services will be offered in the same manner as Aim 1; however, expedited partner treatment will not be an option for syphilis treatment. Standard of Care: Participants will continue to receive syphilis testing per Botswana national guidelines, which includes a VDRL/RPR test at the first ANC visit with delayed results and treatment. Typically, blood specimens are sent to a central lab for processing and results are provided to clinic staff after at least three days. Women are called to return to the clinic for receipt of results. Test results and treatment are recorded in the patient-held and clinic records.

**Data collection:** For participants in the PoC clinic, acceptability of PoC syphilis testing and receipt of treatment (with dates) will be recorded by study staff in study documents, and the patient-held and clinic records. Participants who decline and reasons for decline will be recorded in study records. For participants in the standard of care clinic, the patient-held and clinic obstetric records will be reviewed to identify receipt and dates of syphilis testing and treatment. We will also abstract obstetric and health information (para, gravida, gestational age, HIV status, antiretroviral treatment) from the records of all participants. At the time of enrollment, participants will be asked to respond to a short interviewer-administered questionnaire to collect basic sociodemographic information and costs incurred related to syphilis testing. Participants will also respond to another short survey on costs during their third trimester, which will be conducted over the phone. Cost-related questions will inquire about travel, overnight lodging, out-of-pocket care costs; and the opportunity costs associated with travel, wait, and appointment times. Participants testing positive will be eligible to participate in a brief semi-structured interview on partner notification and treatment.

**Outcomes:** Our primary outcome is acceptability of syphilis testing at the first ANC visit (proportion tested for syphilis out of all eligible women receiving care in the study clinics during implementation of the study). For participants in the PoC clinic, acceptability will be defined as having a PoC test with recorded results. Those who decline PoC testing will be identified as not accepting and will be included in the denominator. For those in the standard of care, the numerator will be women who receive an RPR/VDRL syphilis test recorded in patient-held or clinic records. The denominator for both groups will be all women attending the study clinic during implementation and eligible for participation (1. Age  $\geq$  15 years, 2. Currently pregnant, 3. Attending first ANC visit, 4. 27 weeks of gestation or less, 5. Will reside

Title: The diagnosis and treatment of *Chlamydia trachomatis* and *Neisseria gonorrhoeae* in pregnant women to prevent adverse neonatal consequences.”

in Gaborone through the time of delivery and 1st postnatal visit, And 6. Mentally competent to understand the informed consent).

Additional outcomes will be related to treatment and costs. We will report the proportion of women who received treatment among those with a reactive syphilis test result. We will assess differences in any treatment, treatment completion, and time to treatment.

The primary cost outcome is the average unit cost per woman tested for each strategy and will include both patient-related costs and healthcare system costs. Healthcare-related cost data will be collected from in-country data sources. Patient data will be collected from the short survey.

**Analysis:** First, comparisons will be made across four groups of participant data: **1)** participants in the standard of care clinic enrolled as part of the CT/NG study prior to implementation of the syphilis testing sub-study called “Standard of Care pretest” (n=100); **2)** participants in the standard of care clinic enrolled as part of the syphilis testing sub-study called “Standard of Care post-test” (n=200); **3)** participants in the PoC clinic enrolled as part of the CT/NG study prior to implementation of the syphilis testing sub-study called “PoC pretest” (n=100); and **4)** participants in the PoC clinic enrolled as part of the syphilis testing sub-study called “PoC post-test” (n=200).

To assess differences in receipt of syphilis testing, we will use a difference-in-difference (DiD) strategy, which takes the difference between two before and after differences (pre-post-test with comparison).[25] DiD will be performed using a logistic regression model with a variable for whether the individual was in the PoC clinic (PoC), whether or not it is the post period (Post), an interaction variable for the product of those two variables, and covariates. The primary outcome (Y) is the proportion of eligible women who are tested for syphilis at their first ANC visit:

$Y=a+bPoCPoC+bPostPost+bint(Post*PoC)+bcovariates$  Models will also be stratified by HIV status to see if PoC had a differential impact among WLH. Variables for which there were significant differences between the intervention and comparison group will be included in multivariable model.

Secondarily, will also assess receipt of treatment using DiD analysis by comparing the pre-test and post-test differences in terms of the proportions of participants who had a reactive test who: 1) received the first dose of treatment, and 2) completed treatment. Prevalence of syphilis will also be reported according to treatment group and HIV status as the proportion of individuals testing positive divided by the number of individuals tested. Exact binomial 95% confidence intervals for prevalence will be estimated. All analyses will be conducted with Stata 17.0 (Stata Corporation, College Station, TX).

To compare differences in costs, recurrent costs will be calculated per test, and capital and training costs will be summed and divided by the number of women tested. Those costs will be added to get an average unit cost for each strategy. For the intervention strategy, we will also calculate the average cost by HIV status at first ANC (i.e. the cost of delivering the dual HIV/syphilis test and the rapid syphilis). We will compare the mean costs using the non-parametric Mann-Whitney U test. For hypothesis 4, patient costs will be summed and an average patient cost will be calculated for each strategy, which will be compared using either the Mann-Whitney U test or Student's t-test. Cost components will be examined to determine key cost drivers and to identify potential efficiencies that could be achieved in future scale-up.

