**Data collection:** Participants will be asked to respond to a survey on socioeconomic characteristics, relationship status and sexual history (e.g. number of condomless sex acts), other risk behaviors (e.g. alcohol use), obstetric/medical history, and prior STI symptoms and treatment in the past year. A sub-set of participants will be asked additional questions on partner notification and treatment experiences postnatally. A data collection instrument will be used to abstract obstetric, and medical information from the patient-held and clinic records, including receipt of syphilis testing, results and titre, and treatment.

The sample of sex partners will participate in a brief semi-structured interview on partner notification and treatment experiences. The sample of stakeholders will participate in a brief semi-structured interview on antenatal diagnostic testing for chlamydia and gonorrhea, point-of-care syphilis testing, and STI expedited partner therapy.

Specific Aim 2: To compare longitudinal neonatal outcomes for pregnant women tested & treated for CT/NG infections with women who received standard antenatal care.

**Methods and Procedures:** Simultaneously with Aim 1, 250 antenatal patients at designated study 'standard of care' clinics will be enrolled as a comparison group receiving the standard care with additional partner services. At standard of care clinics, CT/NG testing will be offered to mothers and neonates at the 1st postnatal visit for all 500 participants to accomplish 2(a): To estimate the frequency of vertical transmission of CT/NG infections and adverse neonatal outcomes and association with maternal testing and treatment. And subaim 2(b): To assess independent factors associated with adverse neonatal outcomes and control for these factors in the analysis. Exposure measures will include maternal sociodemographic, behavioral, obstetric, and medical information, and partner treatment, and adverse perinatal outcomes (e.g. low birth weight).

Title: The diagnosis and treatment of *Chlamydia trachomatis* and *Neisseria gonorrhoeae* in pregnant women to prevent adverse neonatal consequences.”

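### Aim 4: only the PoC post-test group has syphilis treatment recorded by study staff, so better recording can appear in the difference-in-differences as better treatment

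*Protocol*

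**What the plan says.** All references are to Protocol section 3 (Study Design) unless stated.

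- **PoC clinic, post-test** (Specific Aim 4, Data collection): "receipt of treatment (with dates) will be recorded by study staff in study documents, and the patient-held and clinic records".
- **Standard-of-care clinic, post-test** (same paragraph): "the patient-held and clinic obstetric records will be reviewed to identify receipt and dates of syphilis testing and treatment". The Reporting and Treatment paragraph says of routine care: "Test results and treatment are recorded in the patient-held and clinic records". No figure for completeness is given.
- **Both pre-test groups** come from the CT/NG parent study (Specific Aim 4, Methods and Procedures). For the parent study's testing clinics, data are abstracted "from the patient-held and clinic records, including receipt of syphilis testing, results and titre, and treatment" (Specific Aim 1, Data collection). For its standard-of-care clinics, "data will be abstracted from the patient-held and clinic records" (Specific Aim 2, Recruitment/Eligibility).
- **Analysis** (Specific Aim 4): receipt of a first dose and completion of treatment, among women with a reactive test, are secondary outcomes compared by difference-in-differences (DiD). The regression has terms for PoC clinic, post period and their product. Time to treatment is listed as an outcome, but no DiD is stated for it.
- **Coding of absent entries**: for testing, the standard-of-care numerator is limited to tests found in the records (Specific Aim 4, Outcomes). For treatment, no rule is given. The SAP contains no Aim 4 analysis.
- **A common contact already exists**: "Participants will also respond to another short survey on costs during their third trimester, which will be conducted over the phone".

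**The concern.** A DiD removes a measurement error that is the same before and after within each clinic. It cannot remove one that changes in one clinic at the moment the intervention starts. Here the PoC clinic moves from chart abstraction (pre-test) to study-staff recording plus charts (post-test), while the standard-of-care clinic stays on charts. The change of source is fully confounded with the interaction term, and the planned covariates do not measure it.

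If charts miss some treatments that were given, and those women are counted as untreated, the PoC clinic's recorded treatment rises when recording improves, even if care does not. At stake is whether Aim 4 can tell better treatment from better documentation.

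A plain post-period comparison, which is the only form available for time to treatment as the plan stands, is exposed more simply. The comparator's dates come only from charts, so a missing entry there becomes a missing or censored time.

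**Working it through.** The plan states no power, effect size or capture rate for Aim 4, so there is no figure to reproduce.

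**Inputs.** True proportion treated p = 0.59 in all four groups, meaning no PoC effect. This is the proportion of women with a reactive RPR who were treated, as cited in Protocol section 4. Chart capture s = 0.95, 0.90 or 0.80 is assumed, since the documents give no value. Capture in PoC post-test is assumed to be 1. An unrecorded treatment is assumed to be coded as not given.

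**Source by group**

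| Group | Source | Recorded proportion |
|---|---|---|
| Standard of care, pre | charts | p × s |
| Standard of care, post | charts | p × s |
| PoC, pre | charts | p × s |
| PoC, post | study staff and charts | p |

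**Spurious DiD** = (p − ps) − (ps − ps) = p(1 − s).

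| s | Chart-recorded proportion | Spurious risk difference | Spurious interaction odds ratio |
|---|---|---|---|
| 0.95 | 0.560 | 0.59 × 0.05 = 0.03 | 1.13 |
| 0.90 | 0.531 | 0.59 × 0.10 = 0.06 | 1.27 |
| 0.80 | 0.472 | 0.59 × 0.20 = 0.12 | 1.61 |

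If 59% is itself a chart-recorded rate, the true rate is 0.59/s and the spurious differences are 0.03, 0.07 and 0.15.

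**Which group drives it.** The standard-of-care bracket is ps − ps = 0, so stable under-recording there cancels. Had PoC pre-test also been staff-recorded, the result would be (p − p) − (ps − ps) = 0. The bias comes from the switch inside the PoC clinic. In a plain post-period comparison of proportions, by contrast, the bias is p(1 − s) and comes from the comparator.

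**Completion.** Protocol section 7 describes three weekly doses. If each dose is charted independently with probability s (an assumption), a full course is charted with probability s³ = 0.86, 0.73 or 0.51. Completion is then more exposed than first dose.

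**Direction.** The denominator is women with a reactive result, and in chart-based groups the result comes from the same records. If a fraction q of whole records is lost, the proportion is 0.59(1 − q)/(1 − q) = 0.59, with no bias. If reactive results go unrecorded in a fraction u of untreated women, the chart proportion is 0.59/(0.59 + 0.41(1 − u)). This gives 0.615, 0.643 and 0.673 for u = 0.1, 0.2 and 0.3. The spurious DiD is then 0.59 minus these values, or −0.03, −0.05 and −0.08, against PoC.

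**Precision.** Section 7 puts syphilis prevalence below 5%. That means at most about 200 × 0.05 = 10 reactive women per post-test group and 100 × 0.05 = 5 per pre-test group. One missing entry moves a group by 0.10 or 0.20. The DiD standard error is √[0.59 × 0.41 × (1/10 + 1/10 + 1/5 + 1/5)] = 0.38.

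**The case against.** Several stronger readings are tempting, and the documents do not support them.

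- *A reader might infer that missing entries in the comparator drive the bias.* In the DiD they cancel if stable over time. Only a plain post-period comparison has that problem.
- *A reader might infer that the plan counts an uncharted treatment as not given.* It says something like this for testing only. For treatment it is silent, though a numerator taken from charts gives that result by default.
- *A reader might infer that the PoC effect is bound to be inflated.* The direction check shows zero or negative bias is possible when the reactive result is lost too.
- *A reader might carry the DiD argument over to time to treatment.* No DiD is stated there, and a missing date is a missing or censored time, not an untreated woman.
- *A reader might assume a higher true treatment rate.* At 90% the same capture rates give 0.90 × (1 − s) = 4.5, 9 and 18 points, but the only treatment rate the protocol cites is 59%.

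The case for leaving the plan alone also has weight. Chart review covers two records, one of which stays with the woman, so capture may be high. Clinical staff give the treatment, and nothing says study staff observe every later dose. If capture in PoC post-test is c rather than 1, the bias is p(c − s): with c = 0.95 and s = 0.90 it is 0.59 × 0.05 = 0.03. Finally, a standard error of 0.38 exceeds any bias shown here. These points limit the size and priority. They do not remove the difference in source, and imprecision does not correct a bias.

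**Conclusion.** The point holds as a difference in ascertainment that coincides exactly with the Post-by-PoC term, with no rule for unrecorded treatment, no source check and no sensitivity analysis. For first dose, the illustration gives about +3, +6 or +12 percentage points with no true effect. It rests on 59% truly treated everywhere, assumed chart capture of 95%, 90% or 80%, full capture in PoC post-test, and coding unrecorded as untreated. Completion is exposed in the same way and probably more. A bias towards PoC is likely but not certain. Time to treatment is affected through missing or censored comparator dates, outside the DiD. Because the outcomes are secondary and the reactive women few, this is worth correcting at modest priority. It does not touch the CT/NG primary outcome.

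**What to change.** 1. **Ask both post-test groups the same questions.** Add to the planned third-trimester phone survey whether the woman was treated for syphilis, how many doses she had and when. Apply one either-source rule (self-report or record) to both groups. Count treatment within the same fixed window from the first ANC visit, and do not let the call close the window early. Women may enrol at up to 27 weeks, and section 4 cites an average treatment delay of five weeks, so an early call could miss delayed treatment. Report this symmetric post-test contrast beside the DiD; it cannot replace it, because the pre-test groups were not asked.
2. **Use one source for the DiD.** Abstract all four groups from the patient-held and clinic records on one form, and keep the PoC study documents for a sensitivity analysis. State that PoC post-test charts are still partly completed by study staff, so this equalises capture only in part. If chart capture were equal, the spurious effect would be zero and a true effect would shrink by the factor s. For example, an assumed true rise from 0.59 to 0.90 (0.31) would show as 0.279 at s = 0.90 and 0.248 at s = 0.80.
3. **State the coding.** Treat unrecorded treatments and dates the same way in all groups, and vary that coding in a sensitivity analysis.

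The cost is a few questions on an existing call and some analysis wording, with no extra visits. Recorded treatment in the PoC post-test group may come out slightly lower.
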